## 7.2. Definitions

- (*Baseline*) *Genetic variations (aka baseline polymorphisms)* are defined as changes (on the amino acid or nucleotide level) in the subject viral sequence compared to a HBV genotype specific reference viral sequence. The reference sequence to be used is provided in the database. The reference viral sequences to be used are:

Virus	Genotype	NGS genbank accession	NGS isolate name	Sanger genbank accession	Sanger isolate name
HBV	A	X02763	adw2	X02763	adw2
HBV	B	AB219428	PNN3	D00329	pJDW233
HBV	C	GQ924620	M38	AB014362	03D03HCC
HBV	D	AF121240	11066	V01460	ayw
HBV	E	AB106564	GA325	X75657	ayw4
HBV	F	AY090458	70H	X75658	adw4q
HBV	G	AF160501	IG29227	AB064311	USG825
HBV	H	FJ356716	CL150171	AY090460	LAS2523
HBV	I	EU833891	H4536-07		

- *Wild type*: If – at certain position – the amino acid/nucleotide in the subject sequence matches the reference sequence, that is no genetic variation is present at that position, the virus is considered to be wild type at that position.
- *Emerging genetic variation*: If – at certain position - a genetic variation is absent at baseline but present at later time point, the genetic variation is considered to be emerging at that time point. For NGS, emerging will be defined based on the prevalence at baseline and at the later time point. “Absent at baseline” is defined as a prevalence below 1% (<1%). “Present at later point” is defined as a prevalence equal or greater than 15% ( $\geq 15\%$ ) at the later time point.

---

- *Enriched genetic variations*: are exclusively defined for NGS analysis. If – at a certain position – a genetic variation has a prevalence of  $\geq 1\%$  but  $< 15\%$  at baseline and a prevalence of  $\geq 15\%$  at a later time point.

### 7.3. Parameters to Analyze

At specified time points and for each list specified in the section below, the following parameters will be analyzed:

- Number (%) of subjects with a genetic variation at a specific position.
- Number (%) of subjects with a specific genetic variation.
- Number (%) of subjects with genetic variations on amino acid level (at positions of interest) in the HBV core protein, HBV core protein positions (47, 28, 15), HBV core protein positions in HBV genotype (A, B, C, D, E, F, G, H and I), polymerase region, precore mutation and basal core promotor region (nucleotide level for PC and BCP) mutation ( Will be presented in separate report not in the CSR)
- Number (%) of subjects with substitutions on amino acid level (at positions of interest) in the HBV core protein, HBV core protein positions of interest (47, 28, 15), HBV core protein positions in HBV genotype (A, B, C, D, E, F, G, H and I), polymerase region, precore mutation and basal core promotor region (nucleotide level for PC and BCP) mutation
- Number (%) of subjects with treatment-emergent substitutions on amino acid level at end of treatment, at time of failure (in subjects with treatment failure as defined in section 5.3.1), at time of viral breakthrough (in subjects with viral breakthrough as defined in section 5.3.1), t time of viral relapse (in subjects with viral relapse as defined in section 5.3.1) by substitution profile in the HBV core protein position of interest (28, 15)
- Number (%) of subjects with treatment-enriched substitutions on amino acid level at end of treatment, at time of failure (in subjects with treatment failure as defined in section 5.3.1), at time of viral breakthrough (in subjects with viral breakthrough as defined in section 5.3.1), t time of viral relapse (in subjects with viral relapse as defined in section 5.3.1) by substitution profile in the HBV core protein position of interest (28, 15)

The focus will be on genetic variations at a time point, emerging genetic variations and reversion to wild type or baseline state.

Sequence variations will be analyzed and reported on both the nucleotide level (for example for changes in the basal core promotor and precore region) as well as on amino

---

acid (aa) level. In the sequence analysis, sequences will be mapped to the respective genotype specific reference sequences after which nt changes and aa substitutions will be annotated compared to the respective genotype specific reference (see Table in section 7.2). In addition, the X02763 (HBV genotype A), which is the master reference sequence of the HBV db, will be used as universal reference sequence.

All NGS data will be collected using a nt and aa read frequency cut-off of  $\geq 0.01$ . For the analysis of baseline nt changes and/or aa substitutions in terms of prevalence and impact on treatment outcome, a read frequency cut-off of  $\geq 0.15$  will be used. The analysis of treatment-emergent nt changes or aa substitutions will consider nt changes or aa substitutions absent at baseline ( $< 0.01$  read frequency) but present at a read frequency of  $\geq 0.15$  at later time points. Virology analyses based on NGS data will also evaluate treatment-enriched nt changes and aa substitutions, defined as present at baseline with a read frequency  $\geq 0.01$  but  $< 0.15$  and with an increase in read frequency of at least 0.15 post-baseline. A minimum increase in read frequency of 0.15 compared to baseline excludes small, potentially technical variations in the read frequency of minority nt changes and aa substitutions which are not expected to have clinical relevance. In addition, for subjects with treatment failure nt changes and aa substitutions detected with a read frequency  $\geq 0.01$  at baseline, at time of failure and at end of study will be described in a listing. The persistence of treatment-emergent nt changes and aa substitutions will be evaluated using a cut-off of  $\geq 0.15$  and  $\geq 0.01$ .

The applicability of the sequencing approach described here (eg, the 0.01 sensitivity limit) will be assessed during the development program and might be adapted if needed.

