### 7.5.2 Post-Baseline

- ***Time of Viral Breakthrough (if applicable)***

For subjects with viral breakthrough, the incidence of treatment emergent (NGS) and treatment enriched genetic variations will be tabulated in frequency outputs (n, %) and the genetic variations will be listed for all subjects with post-baseline sequencing data.

The return to baseline for subjects with viral breakthrough and treatment-emergent genetic variations at time of viral breakthrough will be tabulated in frequency outputs based on Sanger and NGS data, as well as the treatment-emergent genetic variations in subjects who did not return to baseline.

- ***Other Post-Baseline***

The prevalence of genetic variations at other time points will be tabulated in frequency outputs (n, %), based on Sanger and NGS data (1% and 15% cut-off), and the genetic variations will be listed for all subjects. Time points of specific interest are end-of-treatment and end-of-study.

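### The SAP gives two rules for a treatment-enriched variant that yield different counts, and the planned tables do not say which one applies

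*SAP*

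**What the plan says.** SAP 7.2 (Definitions) states that enriched genetic variations "are exclusively defined for NGS analysis". The rule given there is a prevalence of at least 1% but below 15% "at baseline and a prevalence of" at least 15% at a later time point. No minimum rise is set and no reason is given for the cut-offs.

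SAP 7.3 (Parameters to Analyze) gives its own rule: "Virology analyses based on NGS data will also evaluate treatment-enriched nt changes and aa substitutions, defined as present at baseline with a read frequency" of at least 0.01 but below 0.15, "and with an increase in read frequency of at least 0.15 post-baseline". It also gives a reason: "A minimum increase in read frequency of 0.15 compared to baseline excludes small, potentially technical variations", which the SAP does not expect to be clinically relevant. The Other analysis subsection (numbered 7.1.1, after 7.5.3) repeats both the rule and the reason.

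Two planned outputs use the term:

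- SAP 7.3 lists "Number (%) of subjects with treatment-enriched substitutions on amino acid level at end of treatment, at time of failure", and also at viral breakthrough and viral relapse, on the 28- and 15-position core protein lists.
- SAP 7.5.2 says that, for subjects with viral breakthrough, "the incidence of treatment emergent (NGS) and treatment enriched genetic variations will be tabulated in frequency outputs".

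Neither output says which rule it uses, and no sentence in the SAP says that one section overrides the other.

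**The concern.** Both rules apply to NGS data and share the same baseline band. SAP 7.5.2 also joins the two vocabularies, since it speaks of treatment enriched genetic variations. They therefore read as two definitions of one category rather than as two categories.

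A programmer would naturally turn to the section headed Definitions, which holds the looser rule. The tables would then include changes that 7.3 says it wants to leave out. A programmer who followed 7.3 would produce smaller counts under the same title. The reader of the tables could not tell which had been done.

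The outputs support the resistance part of the study. The protocol (2.1) lists emergence of treatment-associated mutations as a secondary endpoint, and enriched variants are tabulated alongside emergent ones.

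**Working it through.** **Inputs.** Let b be the baseline read frequency and f the later one.

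- Rule A (SAP 7.2): 1% ≤ b < 15% and f ≥ 15%.
- Rule B (SAP 7.3 and Other analysis): 1% ≤ b < 15% and f − b ≥ 15 percentage points.

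**Relation between the rules.** Under rule B, f ≥ b + 15%. Because b ≥ 1%, this means f ≥ 16%, so rule A is also met. Rule B is nested inside rule A, and a disagreement can go only one way.

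**Where they disagree.** A variant is enriched under A and not under B when 15% ≤ f < b + 15%. This band is b percentage points wide, from 1 point at b = 1% to just under 15 points as b approaches 15%. The smallest qualifying rise is 15% − b under A (14 points at b = 1%, 1 point at b = 14%) and always 15 points under B.

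**Worked cases.**

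| Baseline | Later | Rise (points) | Enriched under 7.2 | Enriched under 7.3 |
|---|---|---|---|---|
| 1% | 15% | 14 | yes | no |
| 1% | 16% | 15 | yes | yes |
| 7% | 15% | 8 | yes | no |
| 7% | 21% | 14 | yes | no |
| 7% | 22% | 15 | yes | yes |
| 14% | 15% | 1 | yes | no |
| 14% | 28% | 14 | yes | no |
| 14% | 29% | 15 | yes | yes |

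**Check on a whole-percent grid.** Take b = 1% to 14% and f = 0% to 100%. Rule A accepts f = 15% to 100% for each baseline, which is 86 values, so 14 × 86 = 1,204 pairs. For a given b the values accepted by A only are f = 15% to (b + 14)%, which is b values. Summing, 1 + 2 + … + 14 = 105. Rule B therefore accepts 1,204 − 105 = 1,099 pairs, and no pair is accepted by B only. The grid confirms the direction and shape of the disagreement. It is not an estimate of how many variants in the trial would be affected.

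**The case against.** The strongest reply is that this is a small inconsistency in a descriptive category. Most of that stands.

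- The treatment-emergent definition for NGS (below 1% at baseline, 15% or more later) is the same in 7.2, 7.3 and Other analysis. Enriched variants are an additional category, and the focus stated in 7.3 names emerging variations and reversion, not enrichment.
- The outputs are counts and listings, with no test attached. No primary result, arm decision or stopping rule uses the label.
- For subjects with treatment failure, a listing will show all changes at a read frequency of 0.01 or more at baseline, failure and end of study. For those subjects and times either classification could be rebuilt.
- SAP 7.3 allows the sequencing approach to be adapted, and a virologist will write a separate report. Neither provision settles which of the two present rules governs the tables in this SAP.

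A reader might infer more than the documents support:

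- **That 7.2 reports assay noise as selection by JNJ-56136379.** The SAP says only that smaller rises are potentially technical, and it gives no assay variance. The band of disagreement includes 14% to 28%, a doubling, and 1% to 15%, a fifteen-fold rise.
- **That the effect runs over 47 core positions.** The enriched table in 7.3 uses the 28- and 15-position lists. SAP 7.5.2 names no list.
- **That placebo+NA arms would show many false enrichments.** Enrichment needs both a baseline and a later sequence. Day 1 samples are sequenced only when HBV DNA is within assay range, and later sequencing may be triggered by the sponsor virologist (SAP 7.1; Protocol 9.3). Two of the four planned placebo+NA arms, about 20 of 40 subjects, enrol patients with HBV DNA below 60 IU/mL at screening. The assay range is not given, so the effect there cannot be sized.

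**Conclusion.** The SAP holds two operative definitions of one term. They are nested rather than mutually exclusive, but they give different counts whenever a later frequency falls from 15% up to but not including b + 15%. The difference is one-directional: programming from 7.2 can only add enriched calls relative to 7.3.

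The consequence is confined to the descriptive treatment-enriched tables in 7.3 and 7.5.2 and any matching listings. How many variants or subjects would change category cannot be known from the documents. The conclusion rests on reading enriched (7.2) and treatment-enriched (7.3) as the same concept, which the shared NGS scope, the shared baseline band and the wording of 7.5.2 all support.

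The point is worth correcting before the tables are programmed, because the SAP itself gives a reason for one of the two rules and none for the other.

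**What to change.** Replace the enriched definition in SAP 7.2 with the one that 7.3 justifies: baseline read frequency of at least 1% and below 15%, and a rise from baseline of at least 15 percentage points. State that this single definition applies to every enriched-variant table and listing, including those in 7.3, 7.5.2 and Other analysis.

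The cost is one SAP sentence. The downside is small: variants that cross 15% on a smaller rise, such as 10% to 24%, are no longer labelled enriched. Because they start at 1% or more, they are not emergent either. The sponsor virologist should confirm that this is intended.

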## **7.4. Positions & Genetic Variations of Interest**

### ***On the nucleotide level:***

In the basal core promotor region:

- 1762 and 1764 (ECoRI numbering will be used)

In the precore region

- 1896 (numbering to be confirmed by DDL)

---

### ***Amino acid level:***

In the HBV core protein (based on putative binding pocket described in Bourne et al, J Virol, 2006; Katen et al, Structure, 2013)

- Long list (n=47): 18, 19, 23, 24, 25, 26, 27, 28, 29, 30, 31, 32, 33, 37, 38, 102, 103, 105, 106, 107, 109, 110, 111, 114, 115, 116, 117, 118, 119, 122, 123, 124, 125, 126, 127, 128, 129, 131, 132, 133, 134, 136, 137, 138, 139, 140, 141

Based on some recent more detailed published structural data (Klumpp et al, PNAS, 2015, Qiu et al, J Med Chem, 2016; Zhou et al, Sci Rep, 2017; Tu et al, Antivir Res, 2017), and some in house structural analysis, a more shortened list of core positions of interest can be defined:

- Short list (n=28): 23, 24, 25, 29, 30, 33, 37, 38, 102, 105, 106, 109, 110, 118, 122, 124, 125, 127, 128, 129, 132, 133, 134, 137, 138, 139, 140, 141
- Short list (n=15): 23, 24, 25, 29, 30, 33, 37, 105, 106, 109, 110, 118, 124, 127, 128.

In the pol/RT protein:

- 169, 173, 180, 181, 184, 194, 202, 204, 236, 250

## **7.5. Analysis Methods**

Frequencies and percentages will be presented at the time points specified above for the specified parameters. The denominator is the number of subjects with sequencing data at the selected time point.

Analysis may be performed by subgroup (see section 2.5) and treatment groups.

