- j. A subject diary will be provided to the subjects in the pharmacokinetic subgroup, and female subjects using hormonal contraceptives (regardless of type and route of administration). These subjects should report the times of study drug intake at home for 1 week prior to their Week 12 and Week 24 visits in this diary.
- k. Complete physical examination, including height, body weight, temperature, skin examination, and other body systems.
- l. Symptom-directed physical examination, including body weight and temperature.
- m. Vital signs include supine systolic blood pressure (SBP), diastolic blood pressure (DBP), and pulse rate.
- n. If blood sampling or vital signs measurement is scheduled for the same time point as ECG recording, the procedures should preferably be performed in the following order: ECG(s), vital signs, blood draw.

- o. Biochemistry samples must be taken fasted for at least 10 hours for measurement of phosphorus, calcium, creatinine clearance, and lipids. Subjects should bring their study drug with them to each visit and have that day's intake at the site.
- p. Creatinine clearance (estimated by the estimated Glomerular Filtration Rate [eGFR], which is calculated by the Modification of Diet in Renal Disease [MDRD] formula) will be assessed.
- q. In case of a positive dipstick result, a urine sample will be set aside for additional examination of the positive parameter (eg, quantification as applicable).
- r. Only applicable to subjects in the pharmacokinetic subgroup and subjects enrolled at a site with an on-site Fibroscan device.
- s. Sequencing on Day 1 (predose) will be performed by default if HBV DNA levels are within the ranges required for the sequencing assay; other samples may be sequenced based on the sponsor virologist's request.
- t. In virologically suppressed subjects, available historical data on HBeAg status before start of NA treatment will be collected in the eCRF.
- u. Quantitative HBeAg assessment will only be performed in subjects who are defined HBeAg-positive at screening based on a qualitative HBeAg assay.
- v. Exploratory serology samples may be analyzed at the sponsor's discretion. Samples may be used to assess virologic or serologic markers of HBV.
- w. Sparse pharmacokinetic sampling will be performed for all subjects. One sample predose at all indicated time points (except on Day 1: one sample 2 hours postdose only). Study drug should be taken on site. The time of study drug intake will be recorded.

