
 
To evaluate efficacy in terms of HBsAg (in all subjects) or HBeAg (in HBeAg-positive subjects only) seroclearance and/or seroconversion.
 
	
 
Proportion of subjects with HBsAg or HBeAg seroclearance (defined as HBsAg or HBeAg negativity, respectively, based on the assay used) during study treatment and follow-up.
 
Proportion of subjects with HBsAg or HBeAg seroconversion (defined as HBsAg or HBeAg negativity and anti-HBs or anti-HBe antibody positivity, respectively) during study treatment and follow-up.
 

 
To evaluate the frequency of subjects with biochemical response.
 
	
 
Proportion of subjects with ALT improvement and normalization during study treatment and follow-up.
 

 
To evaluate the frequency of HBV virological breakthrough.
 
	
 
Proportion of subjects with virological breakthrough during study treatment defined as confirmed on-treatment HBV DNA increase by <math>>1 \log_{10}</math> from nadir level or confirmed on-treatment HBV DNA level <math>>200</math> IU/mL in subjects who had HBV DNA level below the lower limit of quantification (LLOQ) of the HBV DNA assay.
 

 
To evaluate the potential effect of JNJ-56136379 on the pharmacokinetics of NA when coadministered.
 
	
 
Pharmacokinetics of NA when administered as monotherapy or when coadministered with JNJ-56136379.
 

Objectives	Endpoints

 
To evaluate the pharmacokinetics of JNJ-56136379 when administered as monotherapy.
 
To evaluate the potential effect of NA on the pharmacokinetics of JNJ-56136379 when coadministered.
 
To assess changes in the HBV genome sequence.
 
	
 
Pharmacokinetics of JNJ-56136379 when administered as monotherapy or when coadministered with an NA.
 
Emergence of treatment-associated mutations during study treatment and follow-up.
 

Exploratory	

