### **9.3. Sequencing**

Viral genome sequence analysis will be performed to identify pre-existing baseline polymorphisms and to evaluate emergence of mutations associated with JNJ-56136379 and/or ETV or TDF treatment.

Sequencing of the HBV genome will be performed to monitor HBV variants present at the time points indicated in the **TIME AND EVENTS SCHEDULE**. Samples at baseline will be sequenced by default if HBV DNA levels are within the ranges required for the sequencing assay. The sequencing of samples after baseline may be triggered by the sponsor virologist based

on changes in HBV DNA levels observed in each individual subject and the limits of the sequencing assay.

Samples may be used by the sponsor for additional assessments analyzing the serologic and virologic characteristics of the HBV infection and efficacy of the study treatment, including viral genotypic and phenotypic assessments.

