### 7.1. Time Points and Samples

When analyzing virology parameters, the focus will be on genetic variants at

- Time Point of Sequence at Baseline (BLSEQ): Last available pre-dose time point in the study with virology data available
- Time Point of Sequence at end of JNJ-379 treatment (last available on-treatment time point)
- Time Point of Sequence at Viral Breakthrough: time point with virology data available closest to the time point of viral breakthrough (FTPT) See section 5.3.1 for viral breakthrough definition
- Time Point of Sequence at Viral Relapse: time point with virology data available closest to the time point of viral relapse See section 5.3.1 for viral relapse definition
- Time Point of Sequence at End of Study (ESSEQ): last available off-treatment post-baseline time point in the study with virology data available
- Aggregated Post-Baseline Study Period (ASSEQ): entire post-baseline study period, aggregate of all available time points in the study with virology data available

---

- Aggregated Post-Baseline Treatment Period (ATSEQ): entire post-baseline treatment period, aggregate of all available post-baseline time points during the treatment phase with virology data available

The sequencing of samples after baseline may be triggered by the sponsor virologist based on changes in HBV DNA levels observed in each individual subject and the limits of the sequencing assay.

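### Post-baseline resistance percentages not confined to failures are divided by subjects who happen to be sequenced, a group selected on HBV DNA, so they can overstate emergence and shrink the ratio between arms

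*SAP*

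**What the plan says.** SAP 7.5 fixes the denominator for all sequencing frequencies: "The denominator is the number of subjects with sequencing data at the selected time point".

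Who has such data after baseline is not fixed. SAP 7.1 states: "The sequencing of samples after baseline may be triggered by the sponsor virologist based on changes in HBV DNA levels observed in each individual subject". Assay limits are named there as a second factor. Protocol 9.3 gives the same rule. In the Time and Events Schedule, footnote s makes Day 1 sequencing the default if HBV DNA is in assay range; beyond that, "other samples may be sequenced based on the sponsor virologist's request". Both follow-up schedules also leave sequencing to the virologist's request.

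The percentages serve a secondary endpoint in Protocol 2.1: "Emergence of treatment-associated mutations during study treatment and follow-up". SAP 7.3 asks for "Number (%) of subjects with treatment-emergent substitutions on amino acid level at end of treatment, at time of failure", and further at breakthrough and at relapse, with a parallel item for enriched substitutions. Failure, breakthrough and relapse are each limited to subjects with that event; end of treatment is not. SAP 7.5.2 names end of treatment and end of study as time points of particular interest for the prevalence of variations, and SAP 7.1 also defines aggregated treatment and study periods. SAP 7.5 allows analysis by treatment group.

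**The concern.** A post-baseline sequence exists mainly where HBV DNA prompted a request and was high enough for the assay. Viraemia is also the expected consequence of resistance. A well-suppressed subject is unlikely to enter the denominator and in some cases cannot. No passage says which subjects without breakthrough are sequenced, or how unsequenced subjects count. I found no resistance table with ITT or treated subjects as denominator, although SAP 2.1 defines both populations and SAP 5 uses ITT for efficacy.

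At stake is how a secondary endpoint is read between arms. Protocol 1.3.4 links the Arm 1 breakthroughs to expected resistance, and Amendment 4 stopped that arm and limited 250 mg monotherapy. Readers will look to these tables to see whether variants emerge less often at the higher dose or with an NA. A percentage among sequenced subjects does not answer that. In an arm where nobody is sequenced after baseline, it is undefined.

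**Working it through.** The documents state no expected resistance percentage, so there is no figure to reproduce. The check is direct proportions.

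**Inputs from the documents**
- Arm 1 (75 mg monotherapy): b = 5 confirmed breakthroughs among N = 28 (Protocol 1.3.4, as of 6 February 2019). Two more met the threshold but could not be confirmed and are not counted.
- Planned size of a combination arm: N = 30 (Protocol 3.1).

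**Assumptions, because the documents give no figure**
- One breakthrough in the comparison arm, b = 1.
- All breakthrough subjects are sequenced, and a share m of them carries an emergent variant (m = 100%, then 80%).
- No other subject carries a variant.
- A share s0 of the other subjects is sequenced, the same in both arms; range 0% to 100%.

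**Formulas**
- SAP percentage = b·m / [b + s0·(N − b)]
- Per-treated percentage = b·m / N

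**Results for m = 100%** (sequenced counts are expected values)

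| s0 | Arm 1 | Assumed arm | Ratio |
|---|---|---|---|
| 0% | 5/5 = 100% | 1/1 = 100% | 1.0 |
| 10% | 5/(5 + 2.3) = 68.5% | 1/(1 + 2.9) = 25.6% | 2.7 |
| 20% | 5/(5 + 4.6) = 52.1% | 1/(1 + 5.8) = 14.7% | 3.5 |
| 50% | 5/(5 + 11.5) = 30.3% | 1/(1 + 14.5) = 6.5% | 4.7 |
| 100% | 5/28 = 17.9% | 1/30 = 3.3% | 5.4 |

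The per-treated percentages are 17.9% (Clopper-Pearson 95% CI 6.1% to 36.9%) and 3.3% (0.1% to 17.2%) whatever s0 is. The two denominators agree only when everyone is sequenced.

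With m = 80% and s0 = 0, Arm 1 shows 4/5 = 80% against 4/28 = 14.3% per treated subject.

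It is the ratio that shrinks. The gap in percentage points can widen: at s0 = 10% it is about 43 points, against about 15 per treated subject. If s0 differs between arms, the order can even reverse: 20% in Arm 1 and 0% in the other arm would show 52.1% against 100%.

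**The case against.** The strongest reply is that much of this conditioning is intended. Protocol 11.3.2 plans a descriptive account of relevant changes in non-responders. SAP 7.3 and 7.5.2 restrict the failure, breakthrough and relapse tables to subjects with those events. There, the share of sequenced failures who carry a variant is a proper question with a proper denominator. That stands, and those tables should not change.

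A reader might infer that post-baseline sequence data require virological failure. The documents do not say so: the wording is permissive, sequencing samples are scheduled at most treatment visits, and untreated subjects enter with HBV DNA of at least 2,000 or 20,000 IU/mL. Samples from subjects without breakthrough can be requested.

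Per-subject information is also partly available. Breakthrough proportions are tabulated in the ITT population, counts appear beside percentages, and variants are listed by subject. The event behind Amendment 4 was breakthrough, so it is not hidden. These outputs reduce the harm, but breakthrough is a different endpoint from emergence of a variant, and none of them gives an emergence rate per treated subject.

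Finally, simply substituting all treated subjects would create another bias. Under SAP 7.2, an emergent variant must be below 1% at baseline, which needs a baseline sequence. Virologically suppressed subjects, about 40 of 110 per part, enter with HBV DNA below 60 IU/mL, and many may have none. Counting them as negative would treat unevaluable subjects as free of resistance. This stands, and the fix allows for it.

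**Conclusion.** The point holds for post-baseline tables not confined to failures. It is clearest for emergent and enriched substitutions at end of treatment, and extends to end-of-study and aggregated-period frequencies where these are tabulated. There the SAP percentage is selected on viraemia. Under the stated assumptions it lies between 17.9% and 100% for Arm 1 when the per-treated figure is 17.9%.

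A reader might go further and infer that arms with very different resistance rates will all show 100%. That needs no sequencing at all outside breakthrough, which the documents do not state; at 10% or 20% the arms are already clearly apart. Nor do the documents support a 7.5-fold illustration from 7/28 = 25% against 1/30: only 5 cases were confirmed, which gives 5.4-fold, and the 1/30 is an assumption in either case.

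This is a reporting and interpretation problem on a secondary endpoint in an exploratory study. The primary analysis is unaffected. With arms this small the per-treated percentages are themselves imprecise, but they address the right quantity.

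**What to change.** In SAP 7.5, for post-baseline tables not restricted to failures, report per arm and time point:
- the number with an emergent or enriched variant;
- the number sequenced, meaning with evaluable sequences at both baseline and the post-baseline time point;
- the number treated;
- the percentage of sequenced and the percentage of treated subjects.

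Label the second percentage as emergence detected, a lower bound. Show unevaluable subjects as a separate category, including suppressed subjects without a baseline sequence.

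Keep the sequenced denominator for baseline prevalence and for tables restricted to breakthrough, failure or relapse subjects.

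The cost is SAP wording and extra columns, with no new data. The limitation is that the per-treated figure misses variants in subjects who were not sequenced or could not be evaluated, so it must be read as a minimum.
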